9.2.1.4 TIME PERIODS AND DATES

The study period is determined by the launch date of linaclotide, subsequent uptake, and length of time required to accrue a non-trivial number of SCD cases (see case definition above, Section 9.3 *Variables* and Section 9.5 *Study Size* below). The study period starts on the date of linaclotide commercialisation in each of the countries: in Sweden on February 2013, in the UK on May 2013, and in Spain on September 2014.

The end of data collection has been extended to November 2023 in the UK, and December 2018 in Sweden and in Spain, so the study period will include 50 months in Spain, approximately 10 years in the UK and 68 months in Sweden for medical and prescription data accrual, each database's lag time (for collected data to be available in each database, estimated in up to eight months or until August 2019), and seven months for initial data management and additional data collection from GPs (Q3 2019 for Spain and Sweden, and currently planned until Q3 2024 for the UK). Due to delays experienced in accessing data from the Swedish authorities, version 7.0. of the protocol proposed to extend the final delivery of the final report until June 2020. This is because data from Sweden was not anticipated to become available until Q3-Q4 2019. Version 9.0 of the protocol proposed to extend the final delivery of the final report to June 2022. A very low response rate by the UK GPs to questionnaires

sent to them in Q1 2020 to validate SCD diagnosis was observed. This was possibly because of the shut down in the UK due to COVID-19 infections. A decision was made to resend the questionnaire in Q1 2021. The continued COVID-19 related shutdown in the UK necessitated further postponement of resending the questionnaire to GPs. MAH proposed to resend the questionnaires in Q4 2021. When approached on this matter in Q4 2021, the planning manager at CPRD explained that CPRD paused all GP questionnaire studies until further notice due to the shortage of primary care clinical staff in the UK to continue focusing their resources on supporting COVID-19 activities. Version 11.0 of the protocol proposed to re-open UK validation study in October 2022 until January 2023 with planned study report in Q3 2023.

In response to the MAH's proposal, in the preliminary assessment report for the PASS protocol amendment submission (3rd Oct 2022), PRAC requested the MAH to extend the UK observational period up to the most recent possible date in order to include all available data and to revise the data collection period in the milestones accordingly, without further postponement of the final report (Q3 2023). The MAH contacted CPRD to confirm next steps for data extraction and validation study rerun. CPRD required that the MAH submits a new protocol to the CPRD review committee before requesting the new datasets and re-running the validation study. This is due to the change of dataset from CPRD GOLD to CPRD GOLD and CPRD Aurum, and the change of the observational period. The MAH submitted a new protocol to CPRD in April 2023 and expected to receive approval and the new datasets in Q3 2023. However, the actual process from application submission to data access took almost 12 months and the final data cut was eventually delivered in March 2024. The identification of new potential SCD cases as well as the initiation of validation activities have been completed in Q2 2024.

The validation of the diagnosis and SCD cases ended in Q2 2020 in Spain and expected to end in Q3 2024 in the UK. There is no validation study in Sweden. This study period is expected to allow for sufficient follow-up (long-term safety assessment) for those enrolled during the first period after linaclotide launch and for any subpopulations of interest (those with increased risk of SCD) to have the opportunity to accrue a sizable number of subjects for descriptive purposes. Please refer to Section 9.5 *Study Size* and Section 9.7 *Data Analysis* below.

[figure not shown]
The IBS-C cohort entry date for each cohort member will be defined as the date IBS-C criteria are first fulfilled or 01 February 2013 in Sweden, 13 May 2013 in the UK, and 01 September 2014 in Spain (linaclotide launch dates), whichever is the latest.

The follow-up period for each study subject in the IBS-C cohort will be from the cohort entry date to the earliest of the following (end of follow-up date; one day is the minimum follow-up (Figure 1):

- End of the study period
- Disenrollment from the database (date of transfer out of the practice or the PCP or Sweden)
- Date of last data collection for the practice
- Death
- Index date

The baseline period is the ≥ 12 -month period before IBS-C cohort entry date.

Figure 1. Study Periods in Linaclotide PASS

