8.2 OPERATIONAL OBJECTIVES

- To estimate the risk (case-control OR) of SCD (case) among patients with IBS-C (source population) who received linaclotide prescription vs those who did not, controlling for other potential SCD risk factors (socio-demographics, comorbidities [up to 15], co-medications [up to 15] and other potential variables of interest [up to 10])
- To describe the crude incidence of diarrhoea among patients with IBS-C (source population)

If allowed by the results of the cases and controls validation as discussed below:

- To describe the crude incidence of SCD among patients with IBS-C (source population) prescribed linaclotide (first-time users)
- To describe the crude incidence of SCD among patients with IBS-C (source population) prescribed linaclotide (first-time users) who are at increased risk of SCD:
 - o Patients ≥ 65 years
 - o Patients with hypertension, diabetes, or cardiovascular disease diagnostic codes

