9.2.1.1 INCLUSION/EXCLUSION CRITERIA IN THE IBS-C COHORT

Patients in the study will be required to meet the following inclusion criteria:

- Patient meets IBS-C criteria, as identified through the combination of IBS and constipation codes, (please refer to Section 9.3.4 *Validation of the Diagnosis and Safety Endpoints* below and Annex 3) anytime during the study period
- Patient has at least 12 months of computerised records prior to IBS-C cohort entry date
- Patient meets 'acceptable' criteria from CPRD (the patient is permanently registered at the practice or the PCP and has a valid year of birth and gender) at IBS-C cohort entry date (UK); no equivalent criteria for Spain or Sweden.
- Patient is active (i.e., alive and permanently registered at a practice (UK) or a PCP office (Spain) or the national register (Sweden)) at IBS-C cohort entry date

The following exclusion criteria will apply:

- Patient has no follow-up time (for example, transfers out or dies on the date IBS-C criteria are first fulfilled)
- The practice's up-to-standard (UTS) date in CPRD GOLD is later than the IBS-C cohort entry date (UK); no equivalent criteria for CPRD Aurum, Spain or Sweden*.

*Note: For CPRD GOLD, practices meeting pre-defined quality control standards for completeness, continuity, and plausibility are registered as UTS since the date those standards are met. 'Acceptable' and 'up to standard' are two quality flags that will be taken into account when selecting the study cohort in CPRD GOLD in the UK. In CPRD Aurum, there is no equivalent flag for UTS, therefore, only the 'acceptable' flag will be used for cohort selection. In Spain, no such flags exist but the SIDIAP confirmed that given the study will be performed using data from 2014 onwards, all the data included is of good quality for research purposes. In Sweden, the data received has already been through a quality control by the National Board of Health and Welfare. This control includes checking that compulsory variables like personal registration number, hospital, and main diagnosis are reported, and the validity of all variables values tested. Therefore, no additional changes in the inclusion and exclusion criteria will be needed for Spain and Sweden.

Patients meeting IBS-C inclusion criteria (and not meeting exclusion criteria) at the beginning of the study period (see below) will be prevalent IBS-C patients. Patients meeting IBS-C inclusion criteria thereafter will be incident IBS-C patients.

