9.3.3 IBS DIAGNOSIS AND SEVERITY DEFINITION

The target indication of linaclotide is the treatment of moderate-to-severe IBS-C in adults. There are several Read, SNOMED, ICD-9, or ICD-10 codes related to IBS.

GP testimonies gathered during our pilot study, suggests that patients with IBS are frequently assigned IBS codes after other diagnosis have been ruled out and not necessarily during initial consultations, consistent with published research (Harkness EF et al., 2013a and b). Instead, codes of abdominal pain and other abdominal symptoms, suggestive of IBS, and codes of abdominal examinations were mentioned as part of the codes used for these patients. Sometimes, confirmed diagnosis of IBS might not be coded as such and might only remain in the patient's record's notes.

In order to identify potential cases of IBS-C patients using codes, specific IBS-C codes and a combination of an IBS code with a code for constipation will be used. A combination of a code for abdominal pain and at least two abdominal unspecific codes, in addition to a code for constipation will also be used to identify potential cases of IBS-C. [Table 4](#), [Table 5](#) and [Table 6](#) in Annex 3 include a broad list of Read codes, ICD-10, and ICD-9 codes for the identification of patients with IBS with different levels of specificity, as well as codes for constipation to be used in combination.

There are no Read, ICD-9, or ICD-10 codes to indicate the severity of IBS. The most studied and most commonly used tools for measuring IBS severity involve quality-of-life and patient-reported symptom metrics that are not routinely recorded in the computerised databases selected for this study.

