9.5 STUDY SIZE

If we assume a combined population in the UK, Sweden, and Spain of approximately 120 million people (Eurostat, 2014), a prevalence of IBS recorded in primary care of 3.5% (Harkness et al., 2013) and roughly one-third of those corresponding to IBS-C (Tillisch et al., 2005), then the three proposed databases could be expected to include around 216,000 active IBS-C patients. By December 2016, it was estimated that approximately 9,665 patients would have been exposed to linaclotide in the three target databases, for a combined exposure of more than 4,572 patient-years, with the UK contributing approximately 28% of patients, Spain 25%, and Sweden 47%. These estimated number of patients exposed to linalcotide is now expected to be reached by end of December 2017, so the data collection period has been extended accordingly.

Linaclotide clinical trial results (12 and 26 weeks in length) suggest that about 3% of IBS-C patients exposed to placebo and 19.6% of IBS-C patients exposed to linaclotide will experience diarrhoea over those periods, predominantly within the first weeks of initiating therapy. Among them, 4% in the placebo group and 10.1% in the linaclotide-exposed group will experience severe diarrhoea. Therefore, severe diarrhoea was experienced by 0.13% of all IBS-C patients exposed to placebo and by 1.99% of IBS-C patients exposed to linaclotide (Chey et al., 2012; Rao et al., 2012). Other treatments for patients with IBS-C are also associated with diarrhoea, usually of mild severity (Wood, 2012). Information sent to healthcare professionals by the manufacturer of a drug sometimes prescribed for IBS-C patients in the United States (US) warned of very serious diarrhoea complicated with hypovolaemia, hypotension, and syncope that required admission to the hospital and intravenous therapy in approximately one in 2,500 patients (or 0.04%) (Wooltorton, 2004).

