The crude incidence of diarrhoea and the crude incidence of SCD in the full cohort of patients with IBS-C will be described by calculating the proportion of patients experiencing at least one episode of diarrhoea and the proportion of patients experiencing at least one episode of SCD, as well as their corresponding 95% CIs. The crude incidences of diarrhoea and of SCD in the sub-cohorts of patients with prescriptions of linaclotide will be described by calculating the proportions of patients experiencing diarrhoea or experiencing SCD, respectively, among those at risk for each of the time intervals (as determined graphically) since first treatment prescription, as well as the corresponding 95% CIs. Crude incidence density rates (person-time incidence rates) will also be computed with their corresponding 95% CIs. The incidence of SCD will be assessed separately for death subsequent to diarrhoea (≤ 45 days after diarrhoea diagnosis date) due to the seriousness of this complication (deadly SCD).

All incidence and incidence density rates will also be calculated separately for those groups of patients with increased risk of SCD as defined in the objectives: patients ≥ 65 years and patients with hypertension, diabetes, or cardiovascular disease diagnostic codes.

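### Linaclotide started before cohort entry counts as exposure while SCD before entry cannot count as outcome, so users who qualify after launch can join with their highest-risk weeks unobserved

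*Protocol*

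**What the plan says.** **Entry and follow-up (Protocol 9.2.1.4).** Entry is "defined as the date IBS-C criteria are first fulfilled or 01 February 2013 in Sweden, 13 May 2013 in the UK", or 1 September 2014 in Spain ("linaclotide launch dates), whichever is the latest"). Observation starts there: "The follow-up period for each study subject in the IBS-C cohort will be from the cohort entry date to the earliest of the following", followed by the end-of-follow-up events.

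**Outcome (9.3.2).** An SCD case must occur between cohort entry and end of follow-up.

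**Exposure (9.3.2).** Each patient is a current, non-current or never user at index date according to prescription or dispensing history. Nothing limits that history to the time after entry. This user category is a main exposure of interest. Duration of use is also recorded, counted from the first documented prescription.

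**Eligibility (9.2.1.1).** There are two exclusion criteria: no follow-up time, and the CPRD GOLD up-to-standard date. No criterion concerns earlier linaclotide. On the incident group: "Patients meeting IBS-C inclusion criteria thereafter will be incident IBS-C patients".

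**Objectives (8.2).** Two incidence objectives, both conditional on the validation results, concern patients "prescribed linaclotide (first-time users"). The protocol does not define the term.

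**Timing of risk.** Section 9.5 reports from the clinical trials that diarrhoea occurred "predominantly within the first weeks of initiating therapy". Section 9.7.2.1 also describes it as more frequent early in treatment, and plans incidence "among those at risk for each of the time intervals (as determined graphically) since first treatment prescription".

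**The concern.** Outcome and exposure are observed over different windows. Someone who starts linaclotide before the qualifying codes are complete brings that use into the study but not the weeks in which harm was most likely. If an SCD occurred in those weeks, it is not a case. If the patient tolerated the drug and stayed on it, the patient enters as a current user with the early risk already survived.

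The protocol itself makes this sequence credible. Section 9.3.3 reports that "patients with IBS are frequently assigned IBS codes after other diagnosis have been ruled out and not necessarily during initial consultations", and that some confirmed diagnoses stay only in the notes.

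The stake is the main result. Adding late, lower-risk time without the matching early time pulls an elevated ratio towards 1, the unfavourable direction for a safety study. Patients who are not new starters could also be described as first-time users.

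**Working it through.** No figure stated in the protocol is at issue. The check is a reading of the rules, followed by two illustrations of size.

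**1. The rules side by side.** Take linaclotide started at time S and cohort entry at time E, with S before E.
- An SCD between S and E is outside follow-up, so it is not a case (9.2.1.4, 9.3.2).
- At any index date after E, use since S counts as linaclotide history (9.3.2).
- Controls come from the risk set at the case's index date (9.2.1.3), so exposed time before E is not sampled either. What remains is exposed time after E, from which the early weeks are missing.

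**2. Who can be affected.** A patient who meets the criteria before launch enters on launch day, and marketed linaclotide cannot precede that. Only patients who first qualify after launch (the incident group) can have S before E.

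**3. Where this is most plausible.** In Sweden, diagnoses are specialist-only (9.9), while the drug register captures close to all prescriptions from primary care and outpatient specialists (4.7). A primary-care starter can therefore have dispensed linaclotide on record before any qualifying register diagnosis. The ICD-10 rule in Annex 3 needs an IBS or functional-disorder code plus constipation and has no symptom-code route. Section 9.5 projected that Sweden would supply 47% of linaclotide users. In the UK, the Read and SNOMED rules also accept abdominal pain plus two further symptom codes plus constipation, so entry need not wait for an IBS code.

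**4. Illustration A: ratio based on person-time, with delayed entry.** From 9.5, 4,572 patient-years / 9,665 users = 0.473 years, about 24.7 weeks per user. Assume a ratio of 8 in the first 4 weeks and 1.5 for the other 20.7. Let f be the share of users who lose those 4 weeks because they started before entry.
- All users observed from the start: (4 × 8 + 20.7 × 1.5) / 24.7 = 63.05 / 24.7 = 2.55.
- Mixed: [(1 − f) × 63.05 + f × 31.05] / [(1 − f) × 24.7 + f × 20.7].
- f = 10%: 59.85 / 24.3 = 2.46.
- f = 20%: 56.65 / 23.9 = 2.37.
- f = 30%: 53.45 / 23.5 = 2.27.

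**5. Illustration B: proportion of users, without delayed entry.** Let f be the share of users who passed the early weeks before entry, and g the share of users' SCD events that fall in those weeks. If these users stay in the denominator, observed risk / true risk = 1 − f × g. With the comparator unaffected, a true ratio of 3 reads as follows.

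| f | g = 25% | g = 75% |
|---|---|---|
| 5% | 3 × 0.9875 = 2.96 | 3 × 0.9625 = 2.89 |
| 20% | 3 × 0.95 = 2.85 | 3 × 0.85 = 2.55 |
| 50% | 3 × 0.875 = 2.63 | 3 × 0.625 = 1.88 |

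In both illustrations f is assumed, as are g and the ratios of 8, 1.5 and 3. The patient-years and user counts are an early forecast, and 4.8 says later uptake was below target.

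**The case against.** A reader might infer that the protocol has nothing to deal with this, that linaclotide users in general lose their first weeks, and that early incidence in first-time users is understated by the fraction who start before entry. The documents do not support these readings.

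- **Scope.** Patients prevalent at launch cannot be affected, and the UK symptom-code routes allow entry before an IBS code exists. The weeks are lost only for some incident patients.
- **Existing handling.** Duration of use runs from the first documented prescription, and 9.7.2.1 sets rates out by time since first prescription and may split follow-up. These can separate early from established use.
- **Denominators.** Incidence per interval is among those at risk. Someone not yet under follow-up can fairly be read as not at risk, which is delayed entry. The text does not say so explicitly, but neither does it say the opposite. An understatement equal to the pre-entry fraction is therefore not established.
- **Size.** Nothing in the protocol gives the share of pre-entry starters.
- **Level of detail.** A look-back for first-time use could sit in the SAP, and the SCD incidence objectives run only if validation succeeds.

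All of this narrows the point without removing it. Splitting by duration does not recover events before entry. The main exposure is still the user category, which mixes new starters with pre-entry starters. The case and exposure windows are fixed in this protocol, and the case-control contrast is run whatever the validation shows. The separate look at the first six months after launch addresses a different risk profile in prevalent patients, not use before entry.

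**Conclusion.** The point holds for patients who first meet IBS-C criteria after launch. For them the protocol counts linaclotide use before entry but not SCD before entry, and it leaves first-time user undefined. If the linaclotide effect is concentrated early, as the protocol indicates for diarrhoea, including these users in the main category biases an elevated odds or hazard ratio towards 1.

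The size is unknown. With 5% affected, a true 3 reads 2.96 to 2.89, which is negligible. With 20% it reads 2.85 to 2.55. With 50% and most events early it falls to 1.88, which is material. These figures assume no delayed entry. With delayed entry, and assumed ratios of 8 then 1.5, the ratio falls from 2.55 to 2.37 at 20%. If SCD risk did not differ between early and later treatment, the ratio based on person-time would not be biased by this route.

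**What to change.** - **Section 9.3.2:** define the main linaclotide-exposed category as a first linaclotide prescription or dispensing on or after cohort entry. Keep patients with an earlier one as a separate category in the same model, so that nobody is discarded.
- **Section 9.7.2.1:** define first-time users as having no linaclotide record before entry. State that person-time and at-risk denominators use delayed entry.
- **Reporting:** give the number of pre-entry starters, preferably by country, and one sensitivity analysis that includes them in the exposed group.

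The prescription dates are already held. In Spain the exact date is available for the first prescription (9.9), which is the one needed.

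The cost is lower precision in the main contrast. Section 4.8 puts exposure at 1% to 4%. As an extreme case, if half of the users moved to the separate category and exposure among controls fell from 1.0% to 0.5%, Table 3 would require 1,468 pairs instead of 745 to detect an OR of 3. That compares with about 11,800 potential cases before validation (1,468 / 11,800 = 12%). Whether enough remain depends on how many cases are confirmed.

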9.3 VARIABLES

Included patients will be described according to their characteristics and potential confounder information at cohort entry date (and at index date for cases and controls) using data from the baseline period, GP and hospital diagnoses, procedures, and prescription information from each data source:

9.3.1 PATIENT CHARACTERISTICS:

- Age (as continuous variable and categories < 18, 18–64, ≥ 65 years)
- Gender
- Height and weight
- Socioeconomic status¹
- IBS-C prevalent or incident status
- Pregnancy and breast-feeding (when available)²

¹ When possible: CPRD includes Townsend data and the Index of Multiple Deprivation, SIDIAP includes MEDEA index

² Breast feeding cannot routinely be identified from database records.

 - Magnesium-containing antacids
 - H2 blockers
 - Proton pump inhibitors
 - Non-steroidal anti-inflammatory drugs (NSAIDS)
 - Opioids
 - Analgesics
 - Other potential confounders:
 - History of digestive surgery (especially history of cholecystectomy)
 - Gastroenterology clinic referral
 - Bacterial/viral/parasite lab information (positive versus negative or no information)

For prevalence of chronic comorbidities, prior diagnoses, or history of digestive surgery at index date, the patient's entire medical history will be explored.

Patients with IBS-C and SCD (or cases) will be defined as the occurrence during the follow-up period (between IBS-C cohort entry date and end of follow-up date) of any of the following safety outcomes of interest (primary endpoints) subsequent (see below) to diarrhoea, according to diagnostic codes and primary care laboratory test results:

- Dehydration that requires intravenous rehydration
- Dehydration that requires oral rehydration with solutions of electrolytes
- Electrolyte imbalance: potassium (serum potassium levels 3.0–3.5 mEq/L or < 3.0 mEq/L) and sodium (serum sodium levels > 150 mEq/L)
- Oliguria (urine output < 400 mL in 24 h)
- Anuria (urine output < 50 mL in 24 h)
- New onset thromboembolism episodes
- New-onset orthostatic hypotension
- New-onset syncope
- New-onset dizziness
- New-onset vertigo
- Acute renal failure
- Hypovolemic shock
- Hospitalisation due to diarrhoea
- Stupor
- Coma
- Death (death certificates will be requested to confirm the cause of death)

To identify these safety outcomes, diagnostic and procedure codes from electronic medical records will be used. We will employ combinations of diarrhoea and these safety outcomes codes to identify those that should be considered diarrhoea complications (diarrhoea-related suspected events). As the safety outcomes of interest mentioned above can occur in the absence of diarrhoea (for example, electrolyte imbalances are not only complications of diarrhoea), we will only consider those diarrhoea complications occurring between the diarrhoea diagnosis date and 45 days afterwards (beyond that time window, the occurrence of the proposed outcomes could be considered unrelated to the diarrhoea episode already resolved or, alternatively, associated to deficient patient management). A set of code lists is outlined in [Annex 3](#).

For each medication of interest, a patient (cases and controls) will be classified at the index date according to the following user experience (time window of exposure to the medication):

- Current user, if there was a prescription or dispensation of the medication of interest with supply until the index date or supply that ended in the 90 days before the index date.
- Non-current user, if the last prescription or dispensation was issued longer than 90 days before index date
- Never user, if there is no prescription or dispensation history for that medication.

The main exposures or potential risk factors of interest are:

- Linaclotide user experience category as described above
- Laxatives user experience category as described above

Additionally, other variables listed above will be included in the analyses. Duration of medication use for each of the medications of interest will also be used (defined as time since the first documented prescription without discontinuation until the case or control index date).

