Using the latest available information, the sample size across the three countries is approximately 329,000 patients with IBS-C or potential IBS-C, with an exposure to linaclotide rate ranging from 1% to 4%. If the results of the validation of cases are satisfactory with positive predictive value of SCD algorithms in the UK and Spain $\geq 95\%$, information from the whole cohort will be used to estimate risk of developing SCD across the groups of patients with or without linaclotide exposure, under a cohort study design. If the positive predictive values are $< 95\%$, a case-control analysis will be performed. Assuming the percentage of patients exposed to linaclotide among controls is around 1%, a minimum of 401 case-control pairs would be required to detect an $OR \geq 4$ and 745 possible case-control pairs to detect an $OR \geq 3$ with 80% power, under a matched case-control study design. Within the total IBS-C cohort, it is expected to accrue approximately 11,800 algorithm-identified, potential SCD cases. The final number of case-control pairs to be included in the analyses will depend on the performance of SCD algorithms and case validation results and is expected to be sufficient to detect an $OR \geq 3$ at 80% power, given the number of potential SCD cases identified by the algorithms.

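### The 45-day diarrhoea window captures coincidental events at different rates on and off linaclotide and pulls the algorithm-based OR for SCD towards the OR for having a diarrhoea code

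*Protocol*

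**What the plan says.** Under Protocol sections 9.2.1.2 and 9.3.2, a case is an IBS-C patient with a diarrhoea code followed by any one listed outcome. The list runs from dehydration and acute renal failure to new-onset dizziness, vertigo, syncope, thromboembolism and death. Section 9.3.2 concedes that "the safety outcomes of interest mentioned above can occur in the absence of diarrhoea" and offers the time limit as the remedy: "we will only consider those diarrhoea complications occurring between the diarrhoea diagnosis date and 45 days afterwards". Controls (9.2.1.3) are drawn at random from IBS-C patients in the risk set, with no diarrhoea requirement.

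Section 9.5 expects that "about 3% of IBS-C patients exposed to placebo and 19.6% of IBS-C patients exposed to linaclotide will experience diarrhoea over those periods", the trials having lasted 12 and 26 weeks, and that this happens "predominantly within the first weeks of initiating therapy".

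Outcomes are checked by GP questionnaire in the UK and free-text review in Spain (9.3.4), and death certificates are to be requested. For Sweden, section 9.2.1.4 states: "There is no validation study in Sweden". Section 9.7.3.1 adds sensitivity analyses that treat unvalidated events as missing, as cases or as controls.

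**The concern.** The window limits how many unrelated events are caught per diarrhoea episode. It does not equalise the number of windows between exposure groups, because the drug under study opens them. An unrelated dizziness or thromboembolism code becomes a case if a diarrhoea code came up to 45 days before it, and is ignored otherwise. Outcome misclassification can therefore depend on exposure. The limitations in section 9.9 do not mention this.

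The Annex 3 code lists make coincidence realistic. They include history of vertigo, Ménière's disease, thrombosed haemorrhoids, thrombosis prophylaxis and anxiety about fainting, although the new-onset condition should filter out some of these.

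What is at stake is how the main OR may be read. If the coincidental share is material, the OR partly measures the known effect of linaclotide on diarrhoea and not its effect on severe complications. This matters most for the unvalidated Swedish OR and any pooled OR that includes it.

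**Working it through.** **Inputs.** Section 9.5 gives diarrhoea risks of 3% (placebo) and 19.6% (linaclotide). Among those affected, "4% in the placebo group and 10.1% in the linaclotide-exposed group will experience severe diarrhoea", and overall, "severe diarrhoea was experienced by 0.13% of all IBS-C patients exposed to placebo and by 1.99% of IBS-C patients exposed to linaclotide". Section 4.8 gives "approximately 11,800 algorithm-identified, potential SCD cases" in about 329,000 patients. The documents give no background rate of the listed events, no coincidental share and no ratio of coded diarrhoea in the databases.

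**The plan's own figures.** 3% × 4% = 0.12% (stated 0.13%) and 19.6% × 10.1% = 1.98% (stated 1.99%). Both agree within rounding.

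**Window ratio.** 19.6 / 3 = 6.53. With risk-set sampling the case-control OR estimates a rate ratio, so I use this ratio and not the odds ratio of 7.88. It is a trial value against placebo, mostly from early therapy. Section 9.5 says that other IBS-C treatments also cause diarrhoea, so the ratio among study patients is probably smaller.

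**Formula.** Let unexposed patients have true SCD frequency t and coincidental frequency c, with f = c / (t + c). Exposed patients have T·t and R·c, where T is the true SCD ratio and R the window ratio. Then

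expected OR = (T·t + R·c) / (t + c) = (1 - f)·T + f·R.

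This is a weighted average of T and R, so coincidental events always pull the result towards R.

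**True null (T = 1): expected OR = (1 - f) + f·R**

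| f | R = 2 | R = 4 | R = 6.53 |
|---|---|---|---|
| 5% | 1.05 | 1.15 | 1.28 |
| 20% | 1.20 | 1.60 | 2.11 |
| 50% | 1.50 | 2.50 | 3.77 |

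An OR of 3, one of the two effect sizes quoted in section 4.8, would arise with no true effect at f = (3 - 1)/(6.53 - 1) = 36% if R = 6.53, or at f = (3 - 1)/(4 - 1) = 67% if R = 4. At R = 2 it cannot arise.

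**Equal risk per diarrhoea episode (T = R).** Expected OR = R, so there is no bias.

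**T above R.** Using the severe-diarrhoea ratio 1.99/0.13 = 15.3 as a stand-in for T (severe diarrhoea is not SCD), with R = 6.53 and f = 20%: 0.8 × 15.3 + 0.2 × 6.53 = 12.2 + 1.3 = 13.5. This is attenuation.

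**Sensitivity of f to assumptions.** Assume a background rate of any listed event of 1% to 10% per year and one window per patient with diarrhoea. Days 0 to 45 are 46 days, so the chance per window is q = 1 - exp(-rate × 46/365.25), or 0.13% to 1.25%. Then c = 0.03q and the null OR is (t + 0.196q)/(t + 0.03q):

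- t = 0.05% to 0.08% (section 9.5.2): about 1.3 to 3.4.
- t = 0.5% to 1.0% (section 9.5.1): 1.02 to 1.39.

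The answer depends almost entirely on quantities that the documents do not fix.

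**The case against.** A reader might infer that the linaclotide OR must be inflated, by up to 6.5. The documents do not support that. SCD is by definition a complication of diarrhoea, so more diarrhoea should bring more true SCD. With equal risk per episode there is no bias, and the severe-diarrhoea figures in section 9.5 suggest attenuation if anything. Extra true complications that arise through more diarrhoea are a real effect. This objection stands: the direction is conditional.

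A reader might also infer from the yield that false cases dominate: 11,800/329,000 = 3.6%, against 0.05% to 0.08% in section 9.5.2. That does not follow. Those frequencies are conditional and track the required pairs (94/200,000 = 0.047%; 168/200,000 = 0.084%), and follow-up may differ. The model above gives only 0.03q × 329,000, about 12 to 124 coincidental cases at the assumed rates.

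Nor is it right that nothing addresses false positives. PPV measures them, and a PPV of at least 95% is required before the cohort analysis. The missing and control arms in 9.7.3.1 take unvalidated events out of the case group. Death certificates, the new-onset limits and country-specific analysis before pooling also help.

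These safeguards leave gaps:

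- Section 9.3.4 does not specify PPV by exposure. With 1% to 4% exposed, an overall PPV says little about linaclotide users.
- The nested case-control analysis runs whatever the PPV.
- The UK questionnaire asks whether the episode needed medical assistance and then what the patient experienced. It does not ask whether diarrhoea caused the dizziness, vertigo, syncope or thromboembolism, so a coincidental event can be confirmed.
- In Sweden no case can be validated. If applied there, the missing and control arms would remove every case and could not estimate the coincidental share.

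The 47% Swedish share of linaclotide patients in section 9.5 is a forecast for December 2016. Uptake then fell short and the UK data were extended, so it should not be used to size the Swedish contribution.

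**Conclusion.** The point holds as a conditional bias. The case definition captures coincidental events in proportion to how often a diarrhoea code occurs. Linaclotide changes that frequency, and the protocol plans no analysis that estimates the coincidental share by exposure. The algorithm-based OR moves towards the diarrhoea-code OR: up when the true SCD ratio is below it, down when it is above.

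Under a true null with 20% of unexposed cases coincidental, the expected OR is 1.2, 1.6 or 2.1 for a window ratio of 2, 4 or 6.5. The 20% is illustrative, and 6.5 is a placebo-trial figure that is probably high for this cohort. The formula assumes that coincidental events are independent of diarrhoea and linaclotide; the background-rate range further assumes one window per patient with diarrhoea. The documents support neither a fixed upward bias nor a claim that most algorithm cases are false. This is an inexpensive improvement that decides what the Swedish and pooled ORs can support; the 45-day definition itself need not be abandoned.

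**What to change.** Keep the 45-day definition as primary. Add to sections 9.7.3.1 and 9.7.2.2, as sensitivity analyses by linaclotide status and country:

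1. **Remote-window check.** Over all coded diarrhoea episodes in the cohort, not only those of cases, count first-recorded non-fatal component codes in days 0 to 45 and in an equal 46-day window remote from the same episode, for example days 91 to 136. Report the excess of the first over the second. Follow-up in section 9.2.1.4 ends at the index date, so state that later records are used for this check.
2. **Restricted-component OR.** Give an additional OR limited to dehydration, acute renal failure, hypovolaemic shock and hospitalisation due to diarrhoea. Show it with and without electrolyte imbalance, which section 9.3.2 itself cites as non-specific. It should not replace the full composite, because section 7 names dizziness and syncope among the presentations of dehydration.
3. **PPV by linaclotide status**, where numbers allow.

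State that the unvalidated Swedish OR, and any pooled OR that includes it, will be interpreted in the light of (1) and (2), and add the mechanism to section 9.9.

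The cost is extra programming on data already held, a short addition to the text, and a wider interval for the restricted endpoint.
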